further for eligibility using the participant eligibility summary (PES). Eligible participants will undergo informed consent procedures and a total of 60 participants will be randomized to the collaborative care intervention (n = 30) or care as usual (n =30) condition. Intervention activity will continue for three months after the ED visit, while follow-up continues for six months after the ED visit. Primary outcomes include feasibility. Secondary outcomes include substance use measured by days of use of opioids as well as utilization of healthcare services including ED visits, primary care visits, mental health visits and substance use treatment visits.

1. Aims and Hypotheses

- 1) The primary aim** of the investigation is to determine the feasibility of the collaborative care intervention initiated from the ED and delivered longitudinally. Taken together, all elements of the intervention are referred to as ED-LINC. Feasibility measures include enrollment rates, retention rates at each outcome and follow-up assessment, intervention completion rates and number and types of contacts made by the interventionist. Feasibility of implementation will also be assessed. Guided by Proctor's taxonomy of implementation outcomes⁷, acceptability, feasibility and fidelity to ED-LINC will be measured.
- 2) The secondary aims** of the study are to determine differences in substance use and health care utilization between the two arms. While the study is not powered to detect a difference as this is a feasibility pilot study, substance use and health care utilization will be measured. Specifically, substance use will be measured utilizing a time-line follow back calendar administered by the research assistant to determine days of heroin or illicit opioid use and days of prescription opioid misuse. Additionally, EDIE will be utilized to determine ED utilization and inpatient admissions across Washington, Oregon, Alaska and other areas that EDIE is active. Participants will provide self-report information on primary care visits, mental health and substance use treatment visits. Engagement in substance use treatment will be confirmed via phone by study staff at all periods of assessment.

2. Participants

a. Inclusion Criteria:

- Aged 18-65
- Patients with at least one risk factor for opioid use disorder via the EMR pre-screen

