- Patients with score of ≥ 4 on the NIDA modified ASSIST for illicit opioids (e.g. heroin) OR a score of ≥ 4 on the NIDA modified ASSIST for prescription opioids
- Currently have a phone
- Able to provide a phone number and one additional piece of contact information

b. Exclusion Criteria:

- They are incarcerated or under arrest
- Non-English speaking
- Live beyond a 50 mile radius of HMC
- Require active resuscitation in the ED or other clinical area at the time of RA approach
- Are receiving palliative care services or hospice care for a chronic illness such as metastatic cancer
- Are in the ED or hospital for a primary psychiatric emergency such as suicidal ideation or attempt

- Receiving chronic opioid therapy (COT) defined as prescription opioids for most days out of the last 90 days for a chronic pain condition
- In the ED for sexual assault

3. Recruitment and Retention Estimates

Estimates for the recruitment plan are based on literature related to feasibility studies. Specifically, the sample size of this pilot is related to the pragmatics of recruitment and a sample of n=30 for each group is related to the necessity for examining feasibility including rates of refusal for each group as well as retention in both arms.⁸ Previous work by the research team delivering collaborative care from the ED for patients with injury and prescription drug misuse (ED-LINC 1.0) described excellent recruitment and retention rates of > 80% over six months for subjects getting the intervention.⁹ Therefore the study intends to recruit at least 30 participants per arm with retention rates at each assessment and/or follow-up time point of 80%.

III. STUDY PROCEDURES

A. EMR pre-screen OR staff referral

The study team will be accessing and obtaining PHI from the HMC electronic medical record (EMR) to determine if patients have risk for opioid problems or opioid use disorder. Specifically, each morning a member of the study team will review the current census of patients in the ED and first determine if they are eligible based on criteria listed above easily obtainable (e.g. age, chief complaint) by looking at the track shell using FirstNet. Next, the study team member will look at the EMR for possible eligible participants to see if one of the following items exists in the EMR which are associated with an increased risk of opioid use disorder based on literature:

- Previous overdose
- Diagnosis of OUD in the problem list

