The study team will document how many and what type of consults each patient in the usual care (UC) condition receives. This consultation information will be obtained primarily from the EMR and entered in to REDCap. The team will rely on information from the EMR to ensure completeness and accuracy of all UC documented in REDCap

VIII. INTERIM ANALYSIS PLANS

Interim analysis is not relevant as this is a pilot study and effect sizes are not being measured.

IX. CONTENT AND FREQUENCY OF DSM REPORTS TO NIDA

Annually, the PI ([name]) will submit a grant report (RPPR) to NIDA. The grant report is due in June every year and will include details on:

- Study progress which will include details on feasibility measures, secondary outcomes including substance use and health care utilization and any problems reported to the IRB. An enrollment table will be completed per NIH guidelines
- Responsible conduct of research training received

References

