I. STUDY IDENTIFICATION INFORMATION

TITLE OF PROTOCOL: Emergency Department Longitudinal Integrated Care 2.0 (ED-LINC 2.0)

PRINCIPAL INVESTIGATOR: [name] MD MS

FUNDER OF PROTOCOL: National Institute of Drug Abuse (NIDA)

CLINICALTRIALS.GOV: A description of this clinical trial will be available on <http://www.clinicaltrials.gov>, as required by U.S. Law. **NCT03699085**

SAP Version date: September 2021

Table of Contents:

Summary of Clinical Trial Features.....	Page 3
Primary Outcome Measures.....	Page 4
Refusal Rates	
Follow-up Completion Rates	
ED-LINC Intervention and usual Care process Outcomes	
Implementation Appropriateness	
Satisfaction	
Perception of Care Coordination	
Secondary Outcome Measures.....	Page 5
Substance Use	

Summary of Clinical Trial Features:

The *Emergency Department Longitudinal Integrated Care* (ED-LINC) intervention is a stepped collaborative care model of care initiated from the ED for patients with OUD that combines evidence-based treatment elements, proactive care coordination and population-level outcome tracking. ED-LINC builds upon previous work by tailoring the collaborative care model for patients at high risk for OUD presenting to the ED. A central objective of ED-LINC is to provide evidence-based treatment for OUD and related co-morbidity while in the ED in conjunction with proactive longitudinal care coordination that links patients to ongoing treatment. Weekly caseload supervision with measurement-based care outcome tracking allows for the stepping up of care for patients with recalcitrant symptoms, as well as opportunities to oversee care management linkages to community services targeting the key outcomes of initiation of MOUD and retention in MOUD treatment.

The main objective of this study was to conduct a pilot pragmatic randomized clinical trial of ED-LINC (n=20) compared to usual care (n=20) for ED patients at a single-site at high risk for OUD. The primary outcomes of this study pertain to feasibility of the model, research strategy and implementation.

Primary Outcome Measures

All primary outcome measures used **descriptive statistics**

Refusal Rate was calculated as the number of patients that refused or declined the self-report screening procedure in the ED divided by the eligible number of patients that could have done the self-report screening during the enrollment period.

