Follow-up Completion Rates were calculated for each followup timepoint and were calculated as the number of participants that completed follow-up divided by the total number of participants randomized to each arm of the trial. The 6-month followup completion rate is shown as the number of participants that completed the 6-month self-report interview divided by the number of participants randomized to each arm.

ED-LINC Intervention and usual Care process Outcomes were determined from extensive research notes. Specifically the EDLINC interventionist conducted a process validity assessment and documented the number of unique ED-LINC elements completed for each participant in the intervention.

Implementation Appropriateness was calculated by providing this validated self-report measure to each participant randomized to the ED-LINC assessment. Results were dichotomized to calculate the frequency of participants who 'agreed' or 'completely agreed' that the intervention was 'applicable' and 'seemed like a good match' to document appropriateness.

Satisfaction was calculated using a validated satisfaction questionnaire and provided to all participants at six-months. Each participant will complete the questionnaire and their results will be summed. The median and IQR range will be calculated for participants in each group that complete the assessment.

Perception of Care Coordination will be done using questions from a validated scale. The Wilcoxon Rank Sum test will be used to determine if there are significant differences between groups.

Secondary Outcome Measures

Substance Use

Substance use will be measured using the timeline follow back procedure which is a validated calendar method to determine days of use in a certain calendar period. First, we will sum days of use of illicit opioid use in 30 days at baseline and each followup period for each participant. The mean days of use/30 days with an associated standard deviation will be calculated at each time-period for both the ED-LINC intervention and the usual care control groups.

Next, we will evaluate variance of the data and test model fit on unadjusted data using different distributions. Given previous work, we anticipate the data to be skewed and zero-inflated. Thus, we hypothesize that we may use a normal Gaussian, Poisson or negative binomial distribution.

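### The SAP calls all primary outcomes descriptive, but the only analysis it names for Perception of Care Coordination is a significance test with no between-arm estimate or interval (minor)

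*SAP*

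**What the plan says.** The SAP lists six primary outcomes, and Perception of Care Coordination is one of them in both the table of contents and the section Primary Outcome Measures. That section opens with a general rule: "All primary outcome measures used descriptive statistics". Under Perception of Care Coordination the analysis is: "The Wilcoxon Rank Sum test will be used to determine if there are significant differences between groups". The entry gives no significance level, sidedness, assessment time, scoring rule, summary by arm, difference or interval.

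The neighbouring questionnaire outcome, Satisfaction, is handled differently: "The median and IQR range will be calculated for participants in each group that complete the assessment". No test is attached to it, or to any of the other four primary outcomes.

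On design, Protocol II.B.3 (Recruitment and Retention Estimates) bases the sample size on the practicalities of recruitment and on examining refusal and retention. Protocol II.B.1 (Aims and Hypotheses) says, within the secondary aims: "While the study is not powered to detect a difference as this is a feasibility pilot study". Protocol VIII says: "Interim analysis is not relevant as this is a pilot study and effect sizes are not being measured". Neither document contains a power calculation.

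**The concern.** A test of significance is not a descriptive statistic, so the general rule and the entry for this outcome do not agree as written. The practical question is what the analysis will deliver. A test result without an estimate shows neither how large the difference between arms was nor how precisely it was measured. Protocol II.A says the study is meant to give feasibility information for later studies of ED-LINC. For that purpose a difference with its uncertainty is more useful than a p-value from a sample that was not sized for a comparison.

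**Working it through.** The plan has no power figure to reproduce, so the check asks what the named test could detect at the sample sizes in the documents.

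**Inputs from the documents**
- 20 per arm: SAP, Summary of Clinical Trial Features.
- 30 per arm with 80% retention: Protocol II.B.3.
- About 20% attrition at follow-up: Protocol III, Follow-up Interviews.
- Completers: 20 × 0.8 = 16 per arm and 30 × 0.8 = 24 per arm. The 16 applies the protocol's retention figure to the SAP's sample size.

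**Assumptions (not in the documents for this outcome)**
- Two-sided 5% level. The SAP's only threshold is 0.05, for stepwise elimination in the substance-use model.
- Normal scores with common SD and a pure shift d in SD units. The scale and its SD are not given.

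**Approximate power.** The Wilcoxon test has asymptotic efficiency 3/π = 0.955 relative to the t-test under normality, so

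power ≈ Φ( d × √(n × 0.955 / 2) − 1.96 ).

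For n = 20, d = 0.5: 0.5 × √9.55 = 1.545; 1.545 − 1.96 = −0.415; Φ(−0.415) = 0.34.
For n = 16, d = 0.5: 0.5 × √7.64 = 1.382; 1.382 − 1.96 = −0.578; Φ(−0.578) = 0.28.

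**Simulation.** The approximation is slightly optimistic at these sizes, so the Mann-Whitney test was also simulated, with 10,000 trials per cell. The simulation standard error is at most √(0.25/10,000) = 0.5 percentage points. The rejection rate under no shift was 4.5% to 4.9%.

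| Per arm | 0.5 SD: simulated / approx. | 0.8 SD: simulated / approx. | 1.0 SD: simulated / approx. |
|---|---|---|---|
| 16 (SAP, 20% attrition) | 26% / 28% | 56% / 60% | 75% / 79% |
| 20 (SAP, no attrition) | 32% / 34% | 67% / 70% | 85% / 87% |
| 24 (protocol, 20% attrition) | 37% / 40% | 75% / 77% | 91% / 92% |
| 30 (protocol, no attrition) | 45% / 47% | 84% / 86% | 96% / 97% |

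**Shift detectable with 80% power:** (1.96 + 0.842) × √(2 / (0.955n)) gives 1.01 SD at 16, 0.91 at 20, 0.83 at 24 and 0.74 at 30 per arm.

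**Chance of missing a true 0.5 SD difference at the SAP's size:** from 1 − 0.34 = 66% (20 per arm, approximate) to 1 − 0.26 = 74% (16 per arm, simulated).

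**What an interval would show.** The approximate 95% half-width for a mean difference is 1.96 × √(2/n): 0.69 SD at 16, 0.62 at 20, 0.57 at 24 and 0.51 at 30 per arm. At every size, an interval centred on zero would still contain differences of 0.5 SD in either direction. An interval makes that visible, and a bare p-value does not.

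**The case against.** The case on the other side has force, and several stronger readings that a reader might infer do not stand.

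- *That the protocol itself declares this test underpowered.* It does not. The sentence on power sits in the secondary aims, which concern substance use and health care utilization, and the protocol never names Perception of Care Coordination as an outcome. The reason it gives, a feasibility pilot, reasonably extends to this test, but that is inference. The power table does not depend on it.
- *That the SAP will yield nothing but a significance verdict.* The general rule can be read as promising descriptive summaries for this outcome too, with the test added. What is missing is narrower: a named summary and a between-arm estimate with an interval.
- *That a non-significant result will be reported as no difference, or that this will be the headline comparison.* Nothing in the documents says either. ED-LINC is built to improve coordination (Protocol III.G), but the SAP says the primary outcomes concern feasibility and names initiation of and retention in medication treatment as the key targets.
- *That a null result would be uninformative altogether.* This is too strong for large effects: at 1.0 SD, power is about 75% to 91% across the three sizes from 16 to 24 per arm.

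A pilot may also run an exploratory test, and the mixed tenses in the SAP make a drafting slip plausible. But this test is not labelled exploratory, and it stands under a rule that it contradicts.

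**Conclusion.** The conflict is in the SAP's text and needs no outside figure: a rule that covers all primary outcomes, and one primary outcome whose only named analysis is a significance test without an estimate. The arithmetic shows why the test adds little. At 0.5 SD, power is about 33% (20 per arm), 26% (16) and 38% (24); at 0.8 SD it is about 67%, 56% and 76%. Non-significance would say little about moderate effects.

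These figures assume a two-sided 5% level and a normal shift. A short scale with tied, ordinal scores could behave differently, and the documents do not allow that to be checked. The difference between 20 and 30 per arm is a separate matter and does not alter the conclusion. Severity is minor.

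**What to change.** Make two changes to the SAP.

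1. Under Perception of Care Coordination, replace the test sentence with: *Medians and IQRs by arm and the Hodges-Lehmann between-arm difference with 95% CI will be reported as an exploratory estimate; no significance claim will be made and an interval that includes zero will not be read as no difference.*
2. In the opening statement of Primary Outcome Measures, change the description to: *descriptive statistics, with an exploratory between-arm estimate for Perception of Care Coordination.*

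The second change is needed because a Hodges-Lehmann interval is itself inferential: it is conventionally obtained by inverting the Wilcoxon test. The first change alone would leave the general statement inaccurate. The same edit should name the assessment time and the score, which the estimate requires.

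If the sponsor prefers to keep the test, the lesser repair is to label it exploratory, state its level, say that non-significance is not evidence of no difference, and amend the opening statement accordingly.

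The cost is two sentences and one extra statistic, with no new data. The sponsor gives up a p-value.

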After reviewing eligibility criteria as described above, a study team member will go to the Emergency Department (ED) at HMC. First, appropriateness of the study for the participant will be determined by discussing with a member of the care team if possible (e.g. physician or nurse) and determining if the patient has an appropriate mental status for screening. The study team member will then introduce themselves to the patient and gauge interest in hearing more about the screen. Specifically, the study team member will let the patient know that they are here with 'ED-LINC, a project being conducted out of the Emergency Department at Harborview and can I ask you a few questions to see if you are a good fit for our project'. Once verbal consent is obtained, the study team member will proceed with self-report screening which includes the NIDA m-ASSIST for illicit opioids and prescription opioid misuse.¹⁰ Participants who endorse any use of illicit opioids and/or misuse of prescription opioids in the past 3 months AND have a score of ≥ 4 on the ASSIST are eligible for enrollment.

A member of the research team will then complete the patient eligibility summary (PES) that includes the following:

- NIDA modified-ASSIST for illicit opioids or prescription opioid misuse is ≥ 4 (**yes/no**)
- Between 18-65 years old (**yes/no**)
- English speaking (**yes/no**)
- Medical or injury complaint (e.g. not psych) (**yes/no**)
- Current address is within 50 miles of HMC and valid for six months (**yes/no**)
- Has a cell phone or phone number (**yes/no**)
- Can provide one additional contact (**yes/no**)
- Not currently receiving hospice or palliative care (**yes/no**)
- Currently receiving prescribed opioids from a physician for most days out of 90 (**yes/no**).

If all answers in the PES confirm eligibility, the potential participant will be offered the opportunity to hear more about the study. If the patient has a NIDA m-ASSIST score for illicit opioids or prescription opioid misuse ≥ 4 but is otherwise ineligible, they will be provided a resources list (see Resources Hand Out). More information on informed consent can be found in Section IV Human Subjects Protocol.

C. Obtaining written Informed Consent for those with positive OUD screen and confirmed eligibility on the PES

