The study team member will provide an overview of the study and provide an unsigned copy of the informed consent to the potential participant, allowing ample time to read. If the patient is interested in participating, the study team member will review the informed consent verbally with the participant, answer any questions and obtain a signature on the consent form located in RedCap. If a patient does not want to consent to the study, the study team member will politely inquire rationale behind the refusal and this will be tracked as part of the main outcome related to feasibility. In previous studies, reasons for refusal at this point have included 'too much pain', 'not interested', 'do not want to do follow-up surveys and/or other study procedures' and 'discharged and don't want to wait'.

D. Randomization

After participants have undergone informed consent, the randomization procedure will take place. The investigation will employ a blocked randomization strategy with random assignment of block size of either 4 or 6 participants. Randomization will also be stratified by inclusion for prescription opioid misuse based on a NIDA m-ASSIST score of ≥ 4 for prescription opioid misuse. It is hypothesized that the majority of participants will screen in for illicit opioid use and stratified randomization will be used to ensure balance of participants with prescription opioid misuse given this is an important but likely small population of participants. Participants will be randomized to the following conditions:

- a. Usual Care control condition
- b. ED-LINC 2.0

Study condition will be assigned using the RedCap randomization module which will be programmed prior to study start by a data analyst. After the study team member obtains informed consent, randomization of condition will be performed using RedCap and the participant will be notified of their random assignment.

E. Baseline Interview

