Medications and pharmacotherapy is an important part of collaborative care. It is hypothesized that many patients will not have primary care and might be experiencing fragmented health care delivery. The pharmacotherapy element will be guided by the principle of ultimately linking to care. First, the RC will address the need for coordinated care. After conducting the BNI (above) The RC will step away from the patient and have a conference with one of the supervisory physicians of the study team. In-line with published HMC protocols, the RC will have a conversation with the participant about take-home naloxone. This conversation will be tailored to participant risk for overdose based on their use of illicit opioids, misuse of prescription opioids or both. Naloxone is distributed in many locations around Seattle without a prescription based on pharmacy collaborative agreements. If the participant desires a prescription, the RC will talk with the treating clinical team or the study physicians.

Next, for participants with prescription opioids, the RC will discuss safely storing prescription opioids and safe disposal of prescription opioids. This conversation will be

guided by resources published on stopoverdose.org and med-project.org which are publically available materials.

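### The SAP counts only illicit-opioid days and drops the protocol's second timeline follow-back count, days of prescription-opioid misuse

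*SAP*

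**What the plan says.** **SAP, Secondary Outcome Measures, Substance Use.** The outcome is built in one step: "we will sum days of use of illicit opioid use in 30 days at baseline and each followup period". The mean and standard deviation by arm and time point, the choice of distribution and the stepwise regression all follow from that single sum. The SAP does not mention prescription-opioid misuse anywhere, and it does not say what *illicit* covers.

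**Protocol, II.B Method and Design.** The outcome is stated broadly: "Secondary outcomes include substance use measured by days of use of opioids".

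**Protocol, II.B.1 Aims and Hypotheses, secondary aims.** The calendar is to be used "to determine days of heroin or illicit opioid use and days of prescription opioid misuse". These are two counts.

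**Protocol, elsewhere.** Prescription misuse runs through the rest of the design:

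- Inclusion criteria (II.B.2.a) join two ASSIST scores by OR: a qualifying score "on the NIDA modified ASSIST for illicit opioids (e.g. heroin) OR a score of" the same size for prescription opioids.
- Screening (III.B) accepts "any use of illicit opioids and/or misuse of prescription opioids in the past 3 months", together with the ASSIST threshold.
- Randomization (III.D) is stratified on prescription misuse "to ensure balance of participants with prescription opioid misuse given this is an important but likely small population of participants".
- Pharmacotherapy (III.G) tailors the naloxone discussion to participants "based on their use of illicit opioids, misuse of prescription opioids or both", and adds a step: "for participants with prescription opioids, the RC will discuss safely storing prescription opioids and safe disposal of prescription opioids".

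**The concern.** The trial recruits and stratifies on a behaviour that its SAP outcome does not count, and the intervention includes a step on prescription opioids. Two kinds of participant would be misrepresented:

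- Someone who misuses prescription opioids and uses no illicit opioids starts at 0 and stays there, whatever happens to the misuse. Such zeros arise from the definition and add to the zero inflation the SAP already expects.
- Someone who moves from illicit to misused prescription opioids shows a fall in the score although the number of days with opioid use is unchanged.

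The SAP therefore cannot show a reduction in prescription misuse, and it can show a gain that is only substitution. A later trial that took its outcome measure from this pilot would inherit the gap.

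**Working it through.** The plan gives no figure for this point that could be reproduced. The check is a comparison of texts, followed by simple arithmetic to show the effect per participant.

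**1. Is the second count really absent?**

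| | Protocol | SAP |
|---|---|---|
| Illicit-opioid days | yes (secondary aims) | yes |
| Prescription-misuse days | yes (secondary aims) | not mentioned |
| Overall statement | opioid days, not limited to illicit (II.B) | illicit only |
| Reason for the difference | – | none given |

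**2. Could *illicit* be meant to include misused prescription opioids?** The SAP does not say so. The protocol keeps the two apart at every relevant point: separate ASSIST scores, and/or wording at screening, a stratum for one of them, and a naloxone discussion that allows for either or both. The broad reading is not supported. Even if it was intended, two analysts could derive different outcomes from the same calendars until it is written down.

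**3. Effect per participant.** Inputs: 20 per arm (SAP, Summary of Clinical Trial Features); 80% retention (Protocol, II.B.3), so 0.8 × 20 = 16 followed up per arm; a 30-day window (Protocol VII.B.2 and SAP). The individual day counts are illustrative.

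| Participant | SAP score | Days of either |
|---|---|---|
| Switches from 20 illicit to 20 misuse days | 20 → 0 | 20 → 20 |
| No illicit use; misuse falls from 20 to 5 days | 0 → 0 | 20 → 5 |

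Shift in one arm's mean = change in that person's score ÷ number analysed.

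- One such switcher: 20/20 = 1.0 day per 30; with 16 followed up, 20/16 = 1.25.
- Ceiling per switcher (all 30 days): 30/20 = 1.5; with 16 followed up, 30/16 = 1.875, about 1.9.
- One improver without illicit use: a fall of 20 − 5 = 15 days that the SAP score does not register, or 15/20 = 0.75 day in the arm mean.

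**4. How many participants?** The documents say only that the prescription group is expected to be small. If between 5% and 30% of an arm misused prescription opioids without illicit use (an assumption), that is 0.05 × 20 = 1 to 0.30 × 20 = 6 people per arm, or 2 to 12 of 40. This number is not the size of the prescription stratum. That stratum can include users of both, and an illicit ASSIST score below 4 does not mean no illicit use.

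**5. Why days of either must count each day once.** With 15 illicit days, 12 misuse days and 7 days of both, the total is 15 + 12 − 7 = 20 days. Adding the counts would give 27.

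**The case against.** The other side accepts the mismatch and disputes its weight.

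- **The practical effect may be small.** The protocol expects most participants to screen in on illicit opioids, excludes people on chronic opioid therapy, and gives no figure for misuse alone or for switching. This stands, and it is why no total effect is claimed.
- **The switcher example is constructed.** The protocol's own illicit count would also go from 20 to 0, correctly. The between-arm contrast moves only if switching differs by arm. Both points are right. In the protocol, however, the companion count would rise from 0 to 20 and reveal the substitution; in the SAP nothing would.
- **An illicit-only count has some basis.** The discussion of medication treatment in the protocol is directed at risk from illicit opioids, and the SAP names starting and staying on such treatment as key outcomes. That could justify a narrower measure, but the SAP does not make the argument.
- **Days of either goes beyond the two counts.** The protocol sets no rule for combining them, and a model added to a SAP dated September 2021 could be post hoc. The total does correspond to the broad statement in II.B, and labelling and dating the addition deals with the timing.
- **The daily data may not be in REDCap.** The protocol records use on specific days on a paper calendar but does not say how opioid type is entered. If only totals were entered, the paper forms would have to be consulted.
- **It is an unpowered pilot.** True, and stratification tends to balance these participants across arms. The SAP nevertheless plans arm means and a regression that includes the intervention, so the outcome should be the one the protocol specified.

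**Conclusion.** The concern holds. Followed exactly, the SAP omits a protocol-specified component from the only secondary outcome it lists, without definition or reason. Confidence in the textual mismatch is high.

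Its numerical effect on the trial's results is unknown. Per participant, one complete switch at 20 days moves an arm mean by 1.0 to 1.25 days per 30, and at most by 1.5 to 1.9. These figures assume 20 per arm, 80% retention for the higher value in each pair, and illustrative day counts. They describe one arm's mean, not the treatment contrast.

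The primary feasibility outcomes do not depend on this point. It is a correction that should be made, not one that threatens the study.

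**What to change.** In the SAP's Substance Use section:

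1. Restore prescription-misuse days per 30 as a second timeline follow-back count.
2. Report three quantities by arm and time point: illicit-opioid days, prescription-misuse days, and days of either with each calendar day counted once.
3. Run days of either through the same planned model as illicit days, labelled as added in the SAP with the date of addition.
4. Define *illicit*.
5. If any analysis remains illicit-only, label it as a narrowing of the protocol outcome and give the reason.

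**Cost.** Revised wording, re-tabulation and one extra model run. No new data should be needed, since the protocol plans both counts and a day-by-day calendar. If daily opioid type was not entered in REDCap, the paper calendars must be read again: at most 40 participants × 4 assessments (baseline, 1, 3 and 6 months) = 160.
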